6.3.3 Clinical Laboratory Evaluations

Observed and absolute change from baseline of continuous clinical laboratory values (chemistry, hematology) for each parameter will be summarized at each scheduled time point in the Safety Population.

Shift tables displaying subject counts and percentages classified by baseline grade and maximum grade by treatment will be provided for chemistry and hematology tests with CTCAE v 4.03 grading in the Safety Population.

Table 12 Laboratory Tests

Hematology Tests	Chemistry Tests
ALC	Albumin
Hemoglobin	Alkaline Phosphatase
Hematocrit	ALT
Basophils (Absolute)	AST
Basophils (%)	Blood Urea Nitrogen
Lymphocytes (Absolute)	Urea
Lymphocytes (%)	Calcium
Monocytes (Absolute)	Chloride
Monocytes (%)	CO2
Neutrophils (Absolute)	Creatinine
Neutrophils (%)	CRP
Eosinophils (Absolute)	Direct Bilirubin
Eosinophils (%)	Glucose
Platelets	Lactate Dehydrogenase
Red Blood Cells	Magnesium
White Blood Cells	Phosphate
	Potassium
	Sodium
	Total Bilirubin

	Total Cholesterol
	Total Protein
	Uric Acid
	TSH
	Free T4
	Adrenocorticotropic Hormone (ACTH)

All laboratory data will be listed by subject. Clinical laboratory values that are out of normal ranges will be flagged in the listing.

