**Table 1: Schedule of Assessments – Dose Escalation (monotherapy and FPT155 + pembrolizumab) (Contd)**

Study Phase	Screening	Cycle 1 (21 Days)					Subsequent Cycles* (21 Days)	EOT Follow-Up	Notes
Cycle Day	Screening	D1	D2	D4	D8	D15	D1	28- and 100- Days Post Last Dose	
Window (Days)	-28			$\pm 1$	$\pm 1$	$\pm 1$	$\pm 3$	$\pm 7$	
CT or MRI	X						X	X	
Archival Tumor Tissue (or Fresh Biopsy if Archival Not Available)	X								In dose escalation cohorts, archival tumor tissue is required. If archival tumor tissue is not available, a fresh biopsy is required prior to treatment. Blocks are preferred, if not available, a minimum of 15 slides are acceptable.
Sample Collection									
Chemistry	X	X	X		X	X	X**	X	All samples are assessed locally. Labs may be drawn up to 24 hours in advance of treatment. Refer to Appendix 1 for additional details.
Hematology	X	X	X		X	X	X**	X	Additional labs may be performed as clinically indicated for patients in the first dose cohort that are hospitalized for the initial infusion or for any patients showing evidence of $\geq$ Grade 2 CRS.
Coagulation	X	X					X	X	
Urinalysis	X	X					X	X	
HBsAg and HCV RNA	X								** During dose escalation, chemistry and hematology panel will be drawn on Day 2, 8 and 15 of Cycles 2 and 3.

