**Table 12: Safety – Statistical Analyses**

Endpoint	Statistical Analysis Methods
Incidence of DLTs, AEs, SAEs, and AEs leading to discontinuation, modifications, and interruptions, and death  AEs will be graded according to CTCAE v4.03.	Frequency distribution of treated patients with AE using the worst CTC grade. Patients will only be counted (1) once at the preferred term level, (2) once at the SOC level, and (3) once in the “Total subject” row at their worst CTC grade, regardless of SOC or preferred term.
Laboratory abnormalities  Laboratory values will be graded according to CTCAE v4.03.	Laboratory shift table using the worst CTC grade on treatment per patient.
ECG abnormality	Frequency distribution of treated patients with post baseline ECG abnormality by visit.

Abbreviations: AE = adverse event; CTCAE = common terminology criteria for adverse events; DLT = dose limiting toxicity; ECG = electrocardiogram; SOC = system organ class.

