**Table 13: Protocol-Required Clinical Laboratory Assessments (Contd)**

Hematology: CBC with differential:	
ANC	lymphocytes (%)
ALC	monocytes (%)
basophils (%)	neutrophils (%)
eosinophils (%)	platelets
hemoglobin	RBC
hematocrit	WBC
NOTES:	

 
• If either AST or ALT is elevated, obtain total serum bilirubin and alkaline phosphatase; repeat daily or other interval, as clinically indicated, until resolved or stable
 
• Additional tests to rule out drug-induced liver injury (eg, abdominal ultrasound, serum GGT, hepatitis serology) may be obtained at any time, if clinically indicated
 
• For WOCBP, a serum pregnancy test will be performed at screening and pregnancy testing will be performed at each subsequent cycle of treatment prior to dosing. Additional serum pregnancy testing may be performed if there is a concern with pregnancy, the patient missed a menstrual period, or did not follow the contraceptive guidance in Appendix 3.
 
• Phase 1a: Additional labs may be performed locally as clinically indicated for patients in the first dose cohort that are hospitalized for the initial infusion or for any patients showing evidence of <math>\geq</math> Grade 2 CRS
 
• Phase 1b: Additional labs may be performed locally as clinically indicated
 
• Samples for PK, PD, and ADA analyses should be submitted to the central laboratory as listed in Table 3 and Table 4. Cytokines will be assessed at a central and/or specialty laboratory, however, may also be performed locally for assessment of CRS.
 
• During dose escalation, a chemistry and hematology panel will be drawn on Day 2, 8 and 15 of Cycles 2 and 3.
 
	

Abbreviations: ALC = absolute lymphocyte count; ALT = alanine transaminase; ANC = absolute neutrophil count; APTT = activated partial thromboplastin time; AST = aspartate transaminase; BUN = blood urea nitrogen; CBC = complete blood count; CO2 = carbon dioxide; CRP = c-reactive protein; GGT = gamma-glutamyltransferase; INR = international normalized ratio; HBsAG = hepatitis B surface antigen; HCV RNA = hepatitis C virus ribonucleic acid; LDH = lactate dehydrogenase; PT = prothrombin time; PTT = partial thromboplastin time; RBC = red blood cell; SGOT = serum glutamic-oxaloacetic transaminase; SGPT = serum glutamic-pyruvic transaminase; WBC = white blood cell.

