5.1 Subject Grouping

Subjects will be grouped according to the actual treatment they received. Subjects with the same dose level from the dose escalation and exploratory in Phase 1a for monotherapy and Phase 1a for combination will be combined for summary.

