6.3 Safety Analyses

Safety analyses will be performed separately for Phase 1a Monotherapy Dose Escalation/Exploration, Phase 1b Monotherapy Dose Expansion, Phase 1a Combination Dose Escalation/Exploration and for all patients combined. AEs, clinical laboratory information, vital signs, ECOG performance status, weight, ECGs, and concomitant medications/procedures will be tabulated and summarized for the Safety Population. In addition, the incidence of DLTs in Phase 1a will be summarized using DLT-Evaluable Population. Unless otherwise specified, all analyses will be performed using the Safety Population.

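### By-dose maximum-grade laboratory tables pool Phase 1a patients sampled 8 times with patients sampled twice in Cycles 2-3, so rates of short-lived abnormalities depend partly on the escalation/exploration mix at each dose

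*SAP*

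**What the plan says.** **Sampling.** Protocol Table 1 (escalation) and Table 2 (exploration/expansion) both schedule chemistry and haematology on Days 1, 2, 8 and 15 of Cycle 1, on Day 1 of later cycles, and at the end-of-treatment visits. Table 1 then adds a footnote for escalation only: "During dose escalation, chemistry and hematology panel will be drawn on Day 2, 8 and 15 of Cycles 2 and 3". The notes to Table 13 in Appendix 1 repeat it. Table 2 has no such footnote. Both tables cover monotherapy and the pembrolizumab combination.

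**Pooling.** SAP 5.1 sets this grouping rule for patients: "same dose level from the dose escalation and exploratory in Phase 1a for monotherapy and Phase 1a for combination will be combined for summary". SAP 6.3 likewise treats escalation and exploration as one safety group: "Safety analyses will be performed separately for Phase 1a Monotherapy Dose Escalation/Exploration".

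**Summary measure.** SAP 6.3.3 specifies: "Shift tables displaying subject counts and percentages classified by baseline grade and maximum grade by treatment will be provided". Protocol Table 12 has the same idea: "Laboratory shift table using the worst CTC grade on treatment per patient".

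Neither document limits the maximum to visits that both parts share, splits the table by part, or allows for the number of draws.

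**The concern.** A patient's maximum grade cannot fall, and can rise, as draws are added. Where patients with different schedules are pooled within a dose, and the proportions differ between doses, the table mixes a drug effect with a sampling effect. The proportions do differ: Protocol 2.3 reports exploration patients at 280 mg and 560 mg as of 1 September 2020 and names no other dose.

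The incidence of laboratory abnormalities is part of the primary Phase 1a safety endpoint (Protocol 3.0). The protocol also wants toxicity beyond the DLT period weighed when the recommended dose is chosen (4.1.1.6), and Cycles 2-3 are the first part of that period. A reader of the study report who compares doses on these tables could take a difference in sampling for a difference in toxicity.

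**Working it through.** The plan gives no total number of draws, so there is no stated figure to reproduce. The count comes from Protocol Tables 1 and 2.

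**Scheduled chemistry/haematology draws**

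| | Escalation | Exploration |
|---|---|---|
| Cycle 1 (D1, D2, D8, D15) | 4 | 4 |
| Cycle 2 | 4 | 1 |
| Cycle 3 | 4 | 1 |
| Cycles 1-3 | 12 | 6 |
| Cycles 1-3, excluding pre-dose Cycle 1 Day 1 | 11 | 5 |
| Cycles 2-3 only | 8 | 2 |

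The ratio is 12/6 = 2.0 over Cycles 1-3 and 8/2 = 4.0 in Cycles 2-3. The chemistry row of SAP Appendix 2, as read here, shows one more mark than Protocol Table 2. The coagulation and urinalysis rows there also have an extra mark, so it is probably a layout effect. If it were a real additional Cycle 1 draw, the ratio would be 12/7 = 1.7.

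**Chance that a scheduled draw falls within a transient episode.** Assume one episode lasting w days, with onset uniform over study Days 1 to 64 (Day 64 is Cycle 4 Day 1), in a patient still on treatment. If successive draws are separated by gaps g, the chance of being caught is the sum of min(g, w) divided by 63.

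- Exploration draws after baseline fall on Days 2, 8, 15, 22, 43 and 64, so the gaps are 1, 6, 7, 7, 21, 21.
- Escalation draws fall on Days 2, 8, 15, 22, 23, 29, 36, 43, 44, 50, 57 and 64, so the gaps are 1, 6, 7, 7, three times over.

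| Episode length w | Escalation | Exploration |
|---|---|---|
| 3 days | 30/63 = 48% | 16/63 = 25% |
| 7 days | 63/63 = 100% | 35/63 = 56% |
| 14 days | 100% | 49/63 = 78% |
| 21 days | 100% | 63/63 = 100% |

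**Effect on a by-dose rate.** Assume the same true 30% risk of one 7-day episode at every dose, found by scheduled draws only:

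- all escalation: 0.30 × 1.00 = 30%
- half and half: 0.30 × (1.00 + 0.556)/2 = 23%
- 20% escalation, 80% exploration: 0.30 × (0.2 + 0.8 × 0.556) = 19%

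The spread from 30% to 19% arises with no dose effect at all.

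**Common visits.** Limited to the visits that both schedules share, the count over Cycles 1-3 is 6 against 6.

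**The case against.** Much of the case for leaving the table alone has force.

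- **Long-lasting events.** The guideline in Protocol Appendix 9 says immune hepatitis usually takes 4-6 weeks to resolve, and that hormone replacement for thyroid dysfunction is usually long lasting. Either schedule would catch such events. This stands. What remains is shorter electrolyte, haematology or mild liver changes, whose frequency the documents do not give.
- **Repeat testing.** Clinically significant values are repeated until they settle (Protocol 8.3.6), and raised transaminases are followed closely (Table 13 notes, Appendix 8). Once an event is detected, its peak is followed similarly in both parts. This narrows the gap in grade, but it does not help with an event that no draw detected.
- **Small numbers.** Appendix 11 counts 10 patients at 280 mg and 7 at 560 mg. In the half-and-half illustration, 10 patients would show 2.3 instead of 3.0 affected, which is under one patient. This stands for those counts, but exploration may reach about 50 patients in all.
- **Other displays.** SAP 6.3.3 also summarises values by visit and lists all results. These are free of the maximum-of-looks effect, but the Cycle 2 and 3 Day 2, 8 and 15 rows will hold escalation patients only, and they do not give worst grade by dose.

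A reader might infer more than the documents support:

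- **That DLT assessment is distorted.** It is not: the 21-day window is Cycle 1, where sampling is identical.
- **That the recommended dose rests on these tables.** It is set by review of all safety, PK and PD data (4.1.1.1, 4.1.1.6), and 560 mg was endorsed in July 2020 (Appendix 11).
- **That 840 mg and 1260 mg will be escalation-only and so look worse.** Exploration may open at any cleared dose (4.1.2), and the Amendment 4 summary describes up to 20 exploration patients for the new levels.
- **That the gap is as wide as 100% against 20% for a 7-day episode.** That figure (7/35) arises only if episodes must both start and resolve within Cycles 2-3, the one interval where the schedules differ.

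**Conclusion.** The point holds in a limited form and merits a change to the SAP. The unequal schedules, the pooling and the maximum-grade summary are all explicit, and nothing in the plan corrects for their combination. The by-dose rate of laboratory abnormalities shorter than about 21 days therefore depends partly on the escalation/exploration mix, for patients still on treatment in Cycles 2-3. Sampling in Cycle 1 and from Cycle 4 onward is equal.

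The draw counts are exact. The capture rates are illustrations that rest on assumed durations, uniform onset, perfect adherence to the schedule and no unscheduled draws; unscheduled repeats would make the true gap smaller. The final mix at each dose is not known from the documents, so the direction and size of any distortion between two particular doses cannot be stated. The effect is on the interpretation of a descriptive primary safety display.

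**What to change.** In SAP 6.3.3, keep the planned all-draws maximum-grade shift table and add one of the following, naming it as the version for comparisons across doses:

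1. the same table shown separately for escalation and exploration within each dose; or
2. a table restricted to scheduled visits common to both schedules: Cycle 1 Days 1, 2, 8 and 15, Day 1 of later cycles, and the end-of-treatment visits, without unscheduled results.

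Unscheduled results should stay out of option 2. An abnormality found on an escalation-only draw prompts repeat tests, and those repeats would bring the unequal ascertainment back in.

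A footnote on the all-draws table should state the different schedules. The cost is SAP wording and one extra table; no new data are needed and patient care does not change. Option 1 gives small cells. Option 2 leaves out some escalation draws, but these remain in the all-draws table and the listings, so no observed toxicity is lost from the report.

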6.3.4 Vital Signs

Vital signs parameters including systolic blood pressure, diastolic blood pressure, pulse, respiration rate, and temperature will be summarized for absolute values and change from baseline by visit and time point for safety population. By-subject listing of vital signs and vital signs during infusion will be provided.

6.3.5 12-Lead ECG

A by-subject listing of 12-lead ECG abnormality (abnormal clinical significant, and abnormal not clinically significant) will be provided.

6.3.6 Other Safety Measures

By-subject listings for physical examinations and pregnancy tests will be provided.

6.4 Pharmacokinetic (PK), [REDACTED] and Immunogenicity Analyses

6.4.1 PK Analysis

The PK parameters calculation will be described in a separate analysis plan, this SAP only present the summary and plot of PK parameters.

The following PK parameters will be derived from concentration-time data for FPT155 when appropriate and applicable to characterize single-dose/multiple dose PK.

[figure not shown]
- Area under the concentration-time curve (AUC)
- Maximum observed concentration (C_{max})
- Trough observed serum concentration (C_{trough})
- Clearance (CL)
- Half-life ($t_{1/2}$)
- Volume of distribution at steady state (Vss)

- C_{max} and C_{trough} as well as the accumulation ratio of C_{max} and C_{trough} for pembrolizumab may be calculated if data are available.

Other parameters, such as dose proportionality, accumulation ratio, attainment of steady state, will also be estimated if the data are available.

Individual and mean (\pm SD) serum FPT155 and pembrolizumab concentration-time data will be tabulated and plotted by dose level, respectively. PK parameters of FPT155 and pembrolizumab will be tabulated and summarized by dose level when appropriate and applicable, respectively.

PK analysis will be performed using PK-Evaluable population. PK parameters will be estimated using standard non-compartmental approaches and summarized by dose level using descriptive statistics including: means, standard deviations, geometric means, geometric CV (%), medians, minimums, and maximums.

6.4.3 Immunogenicity Analysis

The anti-drug antibodies (ADA) will be summarized in immunogenicity analysis for Safety Population. Number and percentage of baseline ADA-positive subjects for FPT155 and pembrolizumab will be summarized by treatment group. A baseline ADA-positive patient is defined as a patient who has an ADA positive sample at baseline.

Number and percentage of FPT155 and pembrolizumab treatment induced ADA-positive subjects after initiation of the treatment will be summarized by treatment group. A treatment induced ADA-positive patient is a patient with at least 1 ADA-positive sample relative to baseline after initiation of the treatment.

By-subject listings of FPT155 and pembrolizumab ADA will be provided

Reference

Agresti, A. and B. Coull (1998). "Approximate is Better than "Exact" for Interval Estimation of Binomial Proportions." *The American Statistician* 52(2): 119-126.

Eisenhauer, E. A., P. Bogaerts, L. H. Schwartz, et al. (2009). "New Response Evaluation Criteria in Solid Tumours: Revised RECIST Guideline (version 1.1)." *European Journal of Cancer* 45: 228-247.

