**Table 3: Dose Escalation (monotherapy and FPT155 + pembrolizumab): Schedule of Pharmacokinetic, Immunogenicity, and Pharmacodynamic Biomarker Specimens to be Submitted to Central Laboratory**

Study Cycle	Study Day	Time Point & Window	Type of Sample
Screening	Screening	Screening (Day-28)	Archival tumor, as specified in Table 1
			Tumor biopsy, as specified in Table 1
			Plasma for PD
			PBMC for PD
Cycle 1	Day 1	≤ 4 hours prior to infusion	FPT155 and/or pembrolizumab PK (serum)
			FPT155 and/or pembrolizumab ADA (serum)
			Plasma for PD
			PaxGene for PD
			ctDNA plasma for PD
			PBMC for PD
	15 ( $\pm$ 10) minutes after end of infusion	15 ( $\pm$ 10) minutes after end of infusion	FPT155 and/or pembrolizumab PK (serum)
			FPT155 PK (serum)
			Plasma for PD
			FPT155 PK (serum)
	2 hours ( $\pm$ 30 min) after the end of infusion	2 hours ( $\pm$ 30 min) after the end of infusion	FPT155 PK (serum)
			Plasma for PD
	6 hours ( $\pm$ 60 minutes) after end of infusion	6 hours ( $\pm$ 60 minutes) after end of infusion	FPT155 PK (serum)
			Plasma for PD
	Day 2	24 hours ( $\pm$ 2 hours) after end of infusion	FPT155 PK (serum)
			Plasma for PD
	Day 4	72 hours ( $\pm$ 1 day) after end of infusion	FPT155 PK (serum)
			Plasma for PD
	Day 8	168 hours ( $\pm$ 1 day) after infusion	FPT155 PK (serum)
			Plasma for PD
			PaxGene for PD
			PBMC for PD
	Day 15	336 hours ( $\pm$ 1 day) after infusion	FPT155 PK (serum)
			Plasma for PD
			PaxGene for PD
			PBMC for PD

**Table 3: Dose Escalation (monotherapy and FPT155 + pembrolizumab): Schedule of Pharmacokinetic, Immunogenicity, and Pharmacodynamic Biomarker Specimens to be Submitted to Central Laboratory (Contd)**

Study Cycle	Study Day	Time Point & Window	Type of Sample
Cycles 2 -6	Day 1	$\leq 4$ hours prior to infusion	Tumor Biopsy (prior to Cycle 3 Day 1 $\pm$ 1 week), as specified in Table 1
			FPT155 PK (serum)
			Pembrolizumab PK (serum) (Cycle 2)
			FPT155 ADA (serum) (Cycles 2, 3, and 5)
			Pembrolizumab ADA (serum) (Cycle 2)
			Plasma for PD (Cycles 2, 3, and 5)
			PaxGene for PD (Cycles 2, 3, and 5)
			ctDNA plasma for PD (Cycle 3)
			PBMC for PD (Cycles 2, 3, and 5)
		15 ( $\pm 10$ ) minutes after end of infusion	FPT155 PK (serum)
		1 hour ( $\pm 15$ minutes) after end of infusion	FPT155 PK (serum) (Cycle 3)
			Plasma for PD (Cycle 3)
Cycles 9, 13, and 17	Day 1	$\leq 4$ hours prior to infusion	FPT155 PK (serum)
			Pembrolizumab PK (Cycle 9)

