### 9.3 Populations for Analyses

The following analysis populations are defined for the study as follows:

Population	Description
Enrolled	All patients who sign informed consent and are registered as enrolled in IVRS/IWRS.
Efficacy Population	All patients who have received any portion of at least one dose of study drug.
DLT-Evaluable Population	All patients enrolled into Phase 1a dose escalation portion of the study who received at least 1 dose of all assigned study drug(s) and remain on study for the 21-day DLT evaluation, or who experienced a DLT before clearing the 21-day DLT evaluation interval.
Safety Population	All patients who have received any portion of at least one dose of any study drug.
Response-Evaluable Population	All patients who met eligibility criteria, received at least one dose of any study drug, have measurable tumor lesions at baseline, and have at least one post-baseline disease assessment unless the death and clinical progressive disease occurred prior to the first post baseline disease assessment.
PK-Evaluable Population	All patients who have received at least one dose of study drug and have had sufficient PK sample for the calculation of at least one PK parameter on at least one Study Day.

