3.2 FPT155 Monotherapy Phase 1b Dose Expansion Objectives and Endpoints

The objectives and endpoints for Phase 1b Monotherapy Dose Expansion are summarized in [Table 6](#).

Table 6 Objectives and Endpoints: FPT155 monotherapy Phase 1b dose expansion

OBJECTIVES	ENDPOINTS
PRIMARY	
Safety	Safety

 To evaluate the safety and tolerability of FPT155 as monotherapy in patients with selected advanced solid tumors treated at the RD 	

 The incidence of AEs, SAEs, clinical laboratory abnormalities, and ECG abnormalities The incidence of treatment discontinuations, modifications, and interruptions due to AEs 	
SECONDARY	
Efficacy	Efficacy

 To evaluate the clinical benefit of FPT155 as monotherapy in patients with selected advanced solid tumors treated at the RD through the analysis of ORR, DOR., PFS, and DCR 	

 ORR, DOR, and PFS Disease Control Rate (DCR) defined as total number of patients with confirmed responses of either CR, PR, or stable disease as determined by the investigator per RECIST v1.1, divided by the total number of patients who are evaluable for a response 	

OBJECTIVES	ENDPOINTS

Pharmacokinetics
 
 • To characterize the PK profile of FPT155 as monotherapy in patients with selected advanced solid tumors treated at the RD 	
Pharmacokinetics
 
The following PK parameters will be derived from concentration-time data for FPT155 when appropriate and applicable.
 
 • AUC • C_{max} • C_{trough} • CL • $t_{1/2}$ • V_{ss} • Other parameters, such as dose proportionality, accumulation ratio, attainment of steady state, will also be calculated if the data are available. 
Assessment of time-dependence of PK, the effect of body weight as well as other covariates on PK, and the exposure-response relationship, when the data allow, will be conducted to determine the appropriate dosing approach (eg, body weight-based or fixed dosing) for future trials.

Immunogenicity
 
 • To characterize the immunogenicity of FPT155 as monotherapy in patients with selected advanced solid tumors treated at the RD 	
Immunogenicity
 
 • Incidence of treatment emergent anti-FPT155 antibody response

EXPLORATORY
 	

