4.4 Safety Population

All patients who have received any portion of at least one dose of any study.

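### ADA incidence is a percentage of the whole Safety Population, which requires no ADA sample, and the tabulated treatment-induced category does not define the treatment-emergent endpoint

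*SAP*

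**What the plan says.** The secondary immunogenicity endpoint in both monotherapy phases (SAP 3.1 and 3.2; Protocol 3.0) is "Incidence of treatment emergent anti-FPT155 antibody response".

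SAP 6.4.3 sets the analysis population: "The anti-drug antibodies (ADA) will be summarized in immunogenicity analysis for Safety Population". It then asks for the number and percentage, by treatment group, of two kinds of patient. The first is baseline-positive: "A baseline ADA-positive patient is defined as a patient who has an ADA positive sample at baseline". The second is treatment-induced: "A treatment induced ADA-positive patient is a patient with at least 1 ADA-positive sample relative to baseline after initiation of the treatment".

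Protocol 9.3 defines the Safety Population as "All patients who have received any portion of at least one dose of any study drug". SAP 4.4 carries the same rule with the last word dropped. Neither asks for an ADA sample. The SAP defines a PK-Evaluable set that does require samples (4.6) but has no ADA counterpart.

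On timing, Protocol Tables 3 and 4 schedule ADA before dosing on Cycle 1 Day 1. On-treatment sampling then starts before dosing at Cycle 2: "FPT155 ADA (serum) (Cycles 2, 3, and 5" and later cycles. Both tables also schedule ADA at the end-of-treatment visits, 28 and 100 days after the last dose. Those visits are not held after consent withdrawal (Protocol 1.1, Treatment and Duration).

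On titer, Protocol 8.9.1 has titers reported for confirmed positives, and Protocol 9.4.4 lists titer range and possible transient or persistent status. SAP 6.4.3 summarizes neither.

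**The concern.** There are two separate problems.

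The first is the denominator. A patient dosed once who yields no later ADA result cannot be shown to be positive, yet counts in the Safety Population. The percentage is diluted wherever this happens. For ORR, SAP 6.2.1 states how unassessed patients are treated. For ADA there is no such sentence, only the population.

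The second is the numerator. Neither document defines treatment-emergent ADA. The nearest category depends on a sample being positive relative to baseline, with no baseline-negative condition and no titer rule. Two competent programmers could produce different counts from the same data.

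Classification matters for this molecule. Protocol 2.2.3 reports ADA in 11/16 and 23/24 rats, and in 7/12 and 2/30 monkeys, with a highly variable effect on serum concentration. Protocol 9.4.3 plans to assess the impact of immunogenicity on exposure by dose level, which needs a clear split between ADA-positive, ADA-negative and untested patients.

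**Working it through.** The documents give no ADA rate, ADA sample size or ADA precision, so there is no stated figure to reproduce. Everything below is illustrative and the assumptions are marked.

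**Denominator**

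Inputs: a Phase 1b cohort of 30 dosed patients (SAP 2.3); m patients with no post-dose ADA result, assumed 0 to 5; rate among tested patients, assumed 20%. The upper value of m borrows the plan's allowance of 30 enrolled for 25 response-evaluable. That allowance concerns tumor response and is only a convenient bound here.

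Reported rate = (rate among tested) × (30 − m) / 30.

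| m untested | tested / Safety N | 20% among tested is reported as | relative change |
|---|---|---|---|
| 0 | 30/30 = 1.000 | 20.0% | 0% |
| 1 | 29/30 = 0.967 | 19.3% | −3.3% |
| 3 | 27/30 = 0.900 | 18.0% | −10.0% |
| 5 | 25/30 = 0.833 | 16.7% | −16.7% |

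In whole patients, with 5 untested and 5 positive, 5/25 = 20.0% (exact 90% CI 8.2% to 37.5%) against 5/30 = 16.7% (6.8% to 31.9%). The gap of 3.3 percentage points equals one patient in 30. The intervals are only for scale; the SAP does not specify one for ADA.

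Small dose groups feel it more. Phase 1a escalation patients who are unevaluable for DLT are replaced (Protocol 7.4) but stay in the Safety Population. With 3 tested, 1 positive and 1 replaced and untested (all assumed), 1/3 = 33.3% becomes 1/4 = 25.0%.

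**Numerator**

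Assume the same 30 dosed and 25 tested, with 5 patients going from negative to positive, 1 baseline-positive with a rise in titer, and k baseline-positive with no change. The SAP wording, "at least 1 ADA-positive sample relative to baseline after initiation of the treatment", admits three readings:

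| Reading | Count | Over 30 | Over 25 |
|---|---|---|---|
| Baseline-negative only | 5 | 16.7% | 20.0% |
| Induced plus boosted | 5 + 1 = 6 | 20.0% | 24.0% |
| Any post-dose positive | 6 + k | 20.0%, 23.3%, 26.7%, 30.0% for k = 0, 1, 2, 3 | – |

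Taking induced plus boosted over tested patients (24.0%) as the target, the figure produced under the SAP text could lie anywhere from 16.7% to 30.0% in this example. The literal reading passes the target once k reaches 2.

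**The case against.** The strongest counter-argument is that little is lost. The study is descriptive, with no hypothesis. No sample size or decision rule uses ADA incidence, and by-subject ADA listings are planned, so a reader could rebuild any split. That stands as a limit on the consequence. It does not settle what the summary table should contain.

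Four stronger readings are tempting, and the documents do not support them.

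- A reader might infer that the SAP classes untested patients as ADA-negative. No sentence says so, and the general rule in SAP 5.2 is no imputation. The dilution comes only from taking the percentage over the full Safety Population.
- A reader might infer that anyone who stops before Cycle 2 is untested. The end-of-treatment visits give such a patient two further planned samples unless consent is withdrawn. Eligibility also requires ECOG 0 or 1 and a life expectancy of at least 3 months. The untested group is therefore mainly early deaths, consent withdrawals and missed visits.
- A reader might infer that only induced ADA is reported and boosted ADA excluded. Baseline positives are also tabulated, and the induced wording can be read to include boosted patients. The fault is an undefined phrase, not a stated exclusion.
- A reader might infer that the endpoint is understated overall. That holds only for the denominator taken alone. The definition can push the other way, as the second table shows.

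**Conclusion.** The point holds in two parts. First, followed as written, SAP 6.4.3 multiplies ADA incidence by tested / Safety N. The direction is downward whenever at least one positive is observed and any treated patient lacks a post-dose result. The size cannot be calculated from the documents. Under the assumed 0 to 5 untested of 30 it runs from nothing to a relative loss of 16.7%, or about one patient in a cohort of 30 at a 20% rate.

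Second, the treatment-emergent endpoint has no matching definition. The tabulated category may omit boosted patients or include unchanged baseline positives, so the net error on the endpoint can have either sign.

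This affects the definition and denominator of a secondary endpoint. It does not touch sample size or error rates. It is worth correcting because the remedy is cheap.

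**What to change.** In SAP section 4, add an ADA-evaluable set: dosed, with a baseline ADA result and at least one post-dose ADA result. Use it as the denominator in 6.4.3. Report by treatment group how many Safety Population patients fall outside it, separating those with no post-dose result from those with no baseline result.

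In 6.4.3, define treatment-emergent ADA as induced (baseline negative, any post-dose positive) plus boosted (baseline positive, with a fold rise in titer fixed in the SAP before database lock). Show the two components as well as the total. The titers are already reported under Protocol 8.9.1, so no new sample or visit is needed.

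The cost is a few lines of SAP text, one extra derived flag and a slightly smaller denominator. The rate in tested patients represents all treated patients only if the untested are similar, which is why the untested count should appear beside it.
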